Participants with an indication for or contraindication to one of the trial drugs may still be randomised to the other trial drug. If a participant allocated to both trial drugs develops a contraindication to one of the trial drugs after randomisation into the trial, then they should discontinue that drug but continue to take the other trial drug. If a patient has to discontinue either or both drugs, they should continue to be followed up in the trial as planned (unless they withdraw from the trial). Patients should remain in follow up until the end of the trial follow up period, even if they discontinue trial drug, unless they withdraw from the trial.

The study will be performed open label. Placebo tablets are not available and masking by encapsulation is too complicated and expensive. However, blinding of outcomes is important to obtain unbiased information about tolerability, safety and efficacy. As such, structured symptom questionnaires, ascertainment of clinical outcomes and MRI analysis will be collected by individuals blinded to treatment allocation.

Treatment Allocation: Participants randomised to start drug will be provided with their allocated drug/s after randomisation at the baseline visit, which they will start on the next day (i.e. day 1, week 1). In the event that there is any delay between receiving the trial tablets and starting the treatment, then the patient will receive a reminder telephone call shortly before the day that the medication should be commenced. The first day of treatment defines day 1, week 1.

Participants will be supplied with trial tablets from the hospital pharmacy to cover a maximum period of six months. Detailed dated instructions on dosing will be provided in the patient pack. The participant will be telephoned between the end of weeks 1 and 2 and between the end of weeks 3 and 4, and other times during drug introduction as necessary, as well as follow-up time points, to ensure they are taking the medication correctly.

Drugs will be provided in their packs as marketed and licensed (i.e unaltered) and dispensed by the participating hospital pharmacy under research protocols.

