7.2 STUDY ASSESSMENTS

Study assessments are shown in **Table 5** below, and in **Figure 2**.

Table 5: Study Assessments

Assessment	Prior to Baseline	Visit 1 Baseline	Week 1-2 FU	Week 3-4 FU	6 month FU	12 month FU
Screening for eligibility and Consent ¹ ;	X^s					
Confirm and document ongoing consent		X^s				
Medical including drug history		X^s				
Assess MR or CT diagnostic scan and send a copy to Edinburgh		X^s				
Randomisation		X^s				
Haematology (full blood count) and Biochemistry (urea, electrolytes, creatinine) – most recent value obtained since time of index stroke is acceptable unless clinical reason to expect change		X^s				
Blood Pressure recorded		X^s				X^{s,*}
Cognitive test: document years of education; Montreal Cognitive Assessment (MOCA)		X^s				
Timed Trail Making Test B		X^s				X^{s,*}
Dispense trial medication ²		X^s			X^s	
Structured questionnaire: symptoms; medication history and IMP tablet adherence			X^s	X^s	X^c	X^c
Structured Q: recurrent vascular events, mRS, TICS, TMOCA, SIS, ZUNG					X^c	X^c
Obtain IQCODE (post/phone) from relative						X^c
Follow-up brain MRI						X^s
Health Economics data: EQ-5D-5L, EQ-VAS						X^c
Adverse event / con meds reporting as necessary			X^s	X^s	X^{s,c}	X^{s,c}

¹Consent will be obtained before the data collection procedures commence or randomisation is performed.

Randomisation occurs at the end of the baseline visit. ^{*}at 12 months in some centres only. ²Dispensing in 3-monthly intervals is allowed. ^sAssessment performed by local site team. ^cAssessment performed by blinded assessor who is part of the central trial team.

SIS=Stroke Impact Scale, TICS= Telephone Interview for Cognitive Status, TMOCA= telephone MOCA.

Medical history: Will be performed by the study researcher and will include details of incident stroke, past medical history, vascular risk factors, medication history and years of education.

Baseline brain MR (preferred wherever possible) or CT: To identify the index stroke or exclude other causes of symptoms, and assess the burden of SVD – this is the clinical scan with T2, FLAIR, T1, T2* and diffusion imaging or CT obtained soon after the presentation with stroke that shows either:

- a recent, relevant (in time and location) acute lacunar infarct,

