Haematology (full blood count) and Biochemistry (urea, electrolytes, creatinine) – most recent value obtained since time of index stroke is acceptable unless clinical reason to expect change		X ^s				
Blood pressure		X ^s				X ^s [‡]
Cognitive test: document years of education; Montreal Cognitive Assessment (MOCA)		X ^s				
Timed Trail Making Test B		X ^s				X ^s [‡]
Dispense trial medication ²		X ^s			X ^s	
Structured questionnaire: symptoms; medication history and IMP tablet adherence			X ^s	X ^s	X ^c	X ^c
Structured questionnaire: recurrent vascular events, mRS, TICS, t-MOCA, SIS, ZUNG					X ^c	X ^c
Obtain IQCODE (post/phone) from relative						X ^c
Follow-up brain MRI						X ^s
Health Economics data: EQ-5D-5L, EQ-VAS						X ^c
Adverse event / con meds reporting as necessary			X ^s	X ^s	X ^{s,c}	X ^{s,c}

[†] Consent will be obtained before the data collection procedures commence or randomisation is performed. Randomisation occurs at the end of the baseline visit.

[‡] at 12 months in some centres only.

² Dispensing in 3-monthly intervals is allowed.

^s Assessment performed by local site team.

^c Assessment performed by blinded assessor who is part of the central trial team.

SIS: Stroke Impact Scale; TICS: telephone interview for cognitive status; t-MOCA: telephone MOCA.

SECTION 4. STATISTICAL PRINCIPLES

Confidence and p values**16 Level of statistical significance**

The results of analyses and comparisons will be shown with $p < 0.05$.

17 Multiplicity

No adjustment will be made for multiplicity.

18 Levels of confidence intervals

The results of analyses and comparisons will be shown with 95% confidence intervals.

19 Adherence

19a Definition: 75% of patients will be able to tolerate trial medication, in at least half dose, up to one year after randomisation (i.e. less than 25% will stop trial medication completely through inability to tolerate the drugs).

19b Adherence presentation: See Table 4.

19c Protocol deviations: Protocol violations will be reported to the sponsor within 24 hours of becoming aware of the violation. Protocol deviations will be recorded in a protocol deviation log with these submitted to the sponsors every 3 months.

19d Protocol deviation presentation: Listing of violations and deviations and their frequency.

20 Analysis populations

Three populations are defined:

1. Intention-to-treat: All consented participants with a primary outcome measure.

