Respiratory	xx (xx.x)	xx (xx.x)	(xx.x, xx.x), p=0.xxx	xx (xx.x)	xx (xx.x)	(xx.x, xx.x), p=0.xxx
Gastrointestinal	xx (xx.x)	xx (xx.x)	(xx.x, xx.x), p=0.xxx	xx (xx.x)	xx (xx.x)	(xx.x, xx.x), p=0.xxx
Genitourinary	xx (xx.x)	xx (xx.x)	(xx.x, xx.x), p=0.xxx	xx (xx.x)	xx (xx.x)	(xx.x, xx.x), p=0.xxx
Secondary	xx (xx.x)	xx (xx.x)	(xx.x, xx.x), p=0.xxx	xx (xx.x)	xx (xx.x)	(xx.x, xx.x), p=0.xxx
Haematological	xx (xx.x)	xx (xx.x)	(xx.x, xx.x), p=0.xxx	xx (xx.x)	xx (xx.x)	(xx.x, xx.x), p=0.xxx
Metabolic/endocrine	xx (xx.x)	xx (xx.x)	(xx.x, xx.x), p=0.xxx	xx (xx.x)	xx (xx.x)	(xx.x, xx.x), p=0.xxx
Musculoskeletal	xx (xx.x)	xx (xx.x)	(xx.x, xx.x), p=0.xxx	xx (xx.x)	xx (xx.x)	(xx.x, xx.x), p=0.xxx
Infection/sepsis	xx (xx.x)	xx (xx.x)	(xx.x, xx.x), p=0.xxx	xx (xx.x)	xx (xx.x)	(xx.x, xx.x), p=0.xxx
Tumour/malignancy	xx (xx.x)	xx (xx.x)	(xx.x, xx.x), p=0.xxx	xx (xx.x)	xx (xx.x)	(xx.x, xx.x), p=0.xxx
Other	xx (xx.x)	xx (xx.x)	(xx.x, xx.x), p=0.xxx	xx (xx.x)	xx (xx.x)	(xx.x, xx.x), p=0.xxx
Total	xx (xx.x)	xx (xx.x)	(xx.x, xx.x), p=0.xxx	xx (xx.x)	xx (xx.x)	(xx.x, xx.x), p=0.xxx

Table 8. Targeted symptoms occurring at any time on treatment on isosorbide mononitrate (ISMN), cilostazol (cil) or both.

Data are number (%); comparison by binary logistic regression.

	ISMN	No ISMN	Difference (p)	Cil	No cil	Difference (p)	ISMN /Cil	No ISMN /Cil	Difference (p)
Headache	xx (xx.x)	xx (xx.x)	(xx.x, xx.x), p=0.xxx	xx (xx.x)	xx (xx.x)	(xx.x, xx.x), p=0.xxx	xx (xx.x)	xx (xx.x)	(xx.x, xx.x), p=0.xxx
Stopped normal activities	xx (xx.x)	xx (xx.x)	(xx.x, xx.x), p=0.xxx	xx (xx.x)	xx (xx.x)	(xx.x, xx.x), p=0.xxx	xx (xx.x)	xx (xx.x)	(xx.x, xx.x), p=0.xxx
Palpitations	xx (xx.x)	xx (xx.x)	(xx.x, xx.x), p=0.xxx	xx (xx.x)	xx (xx.x)	(xx.x, xx.x), p=0.xxx	xx (xx.x)	xx (xx.x)	(xx.x, xx.x), p=0.xxx
Stopped normal activities	xx (xx.x)	xx (xx.x)	(xx.x, xx.x), p=0.xxx	xx (xx.x)	xx (xx.x)	(xx.x, xx.x), p=0.xxx	xx (xx.x)	xx (xx.x)	(xx.x, xx.x), p=0.xxx
Dizziness	xx (xx.x)	xx (xx.x)	(xx.x, xx.x), p=0.xxx	xx (xx.x)	xx (xx.x)	(xx.x, xx.x), p=0.xxx	xx (xx.x)	xx (xx.x)	(xx.x, xx.x), p=0.xxx
Stopped normal activities	xx (xx.x)	xx (xx.x)	(xx.x, xx.x), p=0.xxx	xx (xx.x)	xx (xx.x)	(xx.x, xx.x), p=0.xxx	xx (xx.x)	xx (xx.x)	(xx.x, xx.x), p=0.xxx
Loose stools	xx (xx.x)	xx (xx.x)	(xx.x, xx.x), p=0.xxx	xx (xx.x)	xx (xx.x)	(xx.x, xx.x), p=0.xxx	xx (xx.x)	xx (xx.x)	(xx.x, xx.x), p=0.xxx

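### Week 1-2 and 3-4 symptom questionnaires are collected by site staff who know the allocation, contrary to Protocol 5.5.1, and SAP Table 8 does not separate them from the centrally collected ones

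*Protocol*

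**What the plan says.** Protocol 5.5.1 sets out the masking: "The study will be performed open label. Placebo tablets are not available". It then explains why assessment must be protected: "blinding of outcomes is important to obtain unbiased information about tolerability, safety and efficacy". On that basis it commits to a method: "structured symptom questionnaires, ascertainment of clinical outcomes and MRI analysis will be collected by individuals blinded to treatment allocation". No time point is excluded.

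The schedule in Protocol 7.2 (Table 5) has a row headed "Structured questionnaire: symptoms; medication history and IMP tablet adherence". It is coded s at weeks 1-2 and 3-4, and c at months 6 and 12. SAP Table C repeats the row with the same codes. Its footnote for s reads "Assessment performed by local site team". Code c is the blinded assessor in the central trial team.

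SAP Table 8 is captioned "Targeted symptoms occurring at any time on treatment on isosorbide mononitrate (ISMN), cilostazol (cil) or both". It compares the arms symptom by symptom using binary logistic regression, for each drug against no such drug and for both drugs against neither. It has no split by visit or by who collected the data.

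**The concern.** The protocol accepts an open-label design partly because symptom data are said to be gathered by people who do not know the treatment. If half of the scheduled questionnaires are gathered by people who do know it, the design lacks a property it claims. The gap falls in the month of dose escalation. Protocol 1.2 names headache, palpitations and nausea as side effects that slow escalation is meant to reduce.

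An ever/never endpoint makes the mixture harder to interpret. A positive answer from either source counts, so once the sources are combined, a difference caused by how site staff asked cannot be told apart from a difference caused by the drug. A report could also cite 5.5.1 and describe the whole comparison as blinded.

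SAP Table 8 carries some weight. Its eight symptoms (headache, palpitations, dizziness, loose stools, nausea, bleeding, bruising, falls) all correspond to outcome events in Protocol 10.3.2, which are not recorded as adverse events unless serious and possibly related. SAP Tables 6 and 7 cover serious events only. SAP Table 8 is therefore the one table shell that compares arms on these symptoms when they are not serious.

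**Working it through.** The plan gives no figure to reproduce here. The check is mainly a comparison of texts.

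**1. The statement against the schedule**

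| Contact | Protocol 5.5.1 | Protocol Table 5 and SAP Table C |
|---|---|---|
| Week 1-2 | blinded | local site team (s) |
| Week 3-4 | blinded | local site team (s) |
| Month 6 | blinded | blinded central assessor (c) |
| Month 12 | blinded | blinded central assessor (c) |

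Share outside the statement: 2/4 = 50%, both in the escalation phase.

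**2. Do the site staff know the allocation?** No section calls them unblinded, so this is an inference, but a strong one. Code s also covers randomisation and dispensing. Protocol 6.2 says the calls at weeks 1-2 and 3-4 guide dose escalation, and Protocol 3 says they check that the dose has been raised. Nobody can do this without knowing which drug, if any, the participant takes. The text of Protocol 7.2 describes only the 6 and 12 month follow-up as blinded.

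**3. Do these data reach SAP Table 8?** The table does not name its source, so this too is inferred. Protocol 7.1 and 7.2 name headache, dizziness, palpitations, bleeding and altered bowel habit as questionnaire items, and five of the eight table symptoms match them. Nausea, bruising and falls are not named there, but the questionnaire also invites any other symptom. It asks about interference with daily activities, which matches the table's sub-rows on stopping normal activities. Time on treatment includes weeks 1-4.

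**4. What could it do to the comparison? (illustration only)** Assumed: 363 recruited (SAP Table 2), split equally, so 363/2 ≈ 181 per side; two-sided 5% test (the SAP does not state sidedness); normal approximation; no true drug effect; extra recording in the drug arm only. None of the inflation sizes comes from the documents.

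*Extra points d added directly to the any-time rate p.* Rejection rate = Φ((d − 1.96·SE0)/SE1) + Φ((−d − 1.96·SE0)/SE1), where SE0 = √(2p̄(1−p̄)/n), p̄ = p + d/2, and SE1 = √([p(1−p) + (p+d)(1−p−d)]/n).

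| Control rate | d = 0 | 2 points | 5 points | 10 points |
|---|---|---|---|---|
| 10% | 5.0% | 9.3% | 30.1% | 76.2% |
| 30% | 5.0% | 7.0% | 17.4% | 51.4% |
| 50% | 5.0% | 6.7% | 15.8% | 48.1% |

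*Inflation at the two site contacts only.* Assume 10% reporting at each of four independent contacts.
- Control: 1 − 0.90⁴ = 34.4%.
- Drug arm, 1.25 times at site contacts: 1 − 0.875² × 0.90² = 38.0%; odds ratio 1.17; rejection rate about 11%. A z test at exactly this difference gives p ≈ 0.48.
- Drug arm, 1.5 times: 1 − 0.85² × 0.90² = 41.5%; odds ratio 1.35; rejection rate about 28%; p ≈ 0.16.

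The effect thus runs from slight to large depending on the assumption.

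**The case against.** The strongest reply is that the documents already disclose the arrangement. Both schedules show the codes openly, the text of Protocol 7.2 confines blinded follow-up to months 6 and 12, and SAP section 4c gives the SAP precedence. The SAP's paragraph on minimising bias claims only blinded central assessment of outcomes, and nothing in SAP Table 8 calls its data blinded. This shows that the SAP makes no false claim about that table. It does not correct the sentence in 5.5.1, which remains current and unqualified.

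Second, the mechanism is unproven. The questionnaire is structured, described as validated, and scheduled for every arm including neither drug, which limits free probing. That stands. A reader might infer that site callers will question treated participants harder, so that any difference in SAP Table 8 is inflated. The documents do not support that; they show only that the safeguard is absent.

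Third, the later contacts are no clean standard. Participants know their treatment and report their own symptoms, and the same central questionnaire asks about tablet adherence, so the assessor may learn the allocation. Those who stopped early may have no drug symptoms left to report at month 6 or 12. A reader might conclude that arm comparisons should rest on those months alone, with the any-time result made merely descriptive. That could understate harm in the period when symptoms are expected. This objection stands and shapes the fix.

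Fourth, the table's role is limited. The tolerability criterion in SAP section 26a concerns taking at least half dose, and SAP section 30 presents harms in Tables 6 and 7. Only the bleeding row overlaps a listed secondary safety outcome.

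**Conclusion.** The point holds as an inconsistency with a consequence for analysis. Protocol 5.5.1 claims blinded collection for all symptom questionnaires; the schedules in both documents withhold it from two of four. SAP Table 8 then tests a combined count in which the two sources cannot be distinguished, so a reported difference could partly reflect unblinded elicitation.

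This rests on two inferences, both well supported: that site callers know the allocation, and that SAP Table 8 draws on this questionnaire. The size and direction of any bias cannot be established. The illustrative rejection rates depend wholly on the assumed inflation and on whether it is applied to the any-time rate or only to the site contacts. They also assume that all 363 participants enter each comparison. The design is partial factorial, so some enter only one, and both against neither would have at most about 363/4 ≈ 91 per arm under an equal split. SAP Table 8 uses logistic regression rather than the approximation used here.

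**What to change.** - **Protocol 5.5.1:** limit the statement on blinded symptom questionnaires to months 6 and 12, and state that symptoms in weeks 1-4 are collected by site staff aware of the allocation.
- **SAP Table 8:** keep the any-time comparison and add a note that it includes unblinded site-collected data. Name the data source.
- **SAP Table 8, sensitivity display:** add the same comparison in two blocks, weeks 1-4 (site) and months 6 and 12 (central assessor). Describe only the second as collected by blinded assessors. Add a footnote that participants know their treatment, that the same call covers adherence, and that early symptoms in those who stopped drug may be missed. The second block supplements the any-time result and does not replace it.

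The questionnaire is already scheduled by visit, so no new data collection or change to site calls is needed. With recruitment reported in SAP Table 2, this alters description and display, not conduct. The cost is a longer table and a weaker claim about blinding. The gain is that readers can see whether a difference between arms also appears in the centrally collected data.

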5.5.2 Emergency Unblinding Procedures

If the patient develops a contraindication to the trial medications, the medication should be stopped in line with SPC guidance. Similarly if the patient develops a definite indication for the trial medications the study medications should be stopped as per the SPC.

As this is an open label trial, there should be no need to unblind the allocated treatment. If some contraindication to cilostazol or ISMN develops after randomisation, the trial treatment should simply be stopped as per SPC guidance. If identification of the trial drug is considered necessary, the tablets can simply be examined and identified as cilostazol or ISMN as they will be dispensed in their licensed packaging.

5.5.3 Withdrawal of Study Participants

Participants may withdraw consent at any point. Where participants agree, we will retain the data collected up to the point of withdrawal for analysis. If the participant is willing, we will record the reason for withdrawal. Trial medication may be stopped at any time by the investigator or treating physician if deemed advisable. Stopping trial medication on its own does not necessarily equate with withdrawal from the trial, and follow-up procedures will continue unless the participant withdraws consent. If after randomisation into LACI-2, a participant subsequently is found to have a condition which would have made them ineligible for recruitment, these participants will be retained in the trial, at least for the purposes of follow-up, to protect the 'intention to treat' principle of analysis, and a decision for the continuation of the IMP will be made by the Principal Investigator with the participant or their relatives in the event of loss of capacity on the basis of safety. A recurrent event, such as stroke or other outcome, is not of itself a reason for withdrawal or discontinuation of IMP. The participant's wishes as to continuing trial medication and participation in the event that they lose capacity during the trial will be documented in the trial consent form.

6 INVESTIGATIONAL MEDICINAL PRODUCTS

6.1 STUDY DRUGS

The IMP is defined by the active substance only, therefore all authorised brands may be used. Oral cilostazol or isosorbide mononitrate slow release will be prescribed as per the brand available in the participating hospital pharmacy. Most isosorbide mononitrate preparations are slow release in the UK however, in pharmacies where slow release preparations of isosorbide mononitrate are not available, then non-slow release preparations may be used.

Several doses and brands of these drugs are marketed in the UK, examples are given below.

Oral Cilostazol 100mg tablets, Generics [UK] Ltd t/a Mylan, [name], United Kingdom. (<http://www.mylan.co.uk>)

Oral Isotard® 25 mg XL (Isosorbide Mononitrate) tablets, Kyowa Kirin Limited, [name], United Kingdom. (<http://www.kyowa-kirin.com/kkr/>)

Isosorbide mononitrate (ISMN) 20mg, Pharmavit Ltd, [name] (<http://www.pharmavit.eu>)

Cilostazol and ISMN are both licensed products for treatment of vascular diseases in Europe and the example summaries of the product characteristics are appended to this trial protocol.

6.1.1 Study Drug Identification

The IMP is defined by the active substance only, therefore all authorised brands may be used.

Cilostazol, generic, as 50mg or 100mg tablets.

Isosorbide mononitrate slow release, generic, for example as 25mg XL or 50mg XL tablets to the suggested target dose of 40-60mg daily.

Isosorbide mononitrate, generic, as 20mg tablets to the suggested target dose of 40-60mg daily.

Most isosorbide mononitrate preparations are slow release in the UK. However, where slow release preparations of isosorbide mononitrate are not available, then non-slow release preparations may be used, but the dose should be split half in the morning (e.g. 08.00 am) and half in the evening (e.g. 18.00hrs). Non-slow release preparations may only be available in 20mg tablets in which case the 20mg should be substituted for the 25mg dose. A target dose of ISMN is 40-60mg daily. Detailed prescribing and administration instructions will be provided in the treatment pack.

6.1.2 Study Drug Manufacturer

Details of one manufacturer of each of the trial drugs are given below. All drugs are available from several providers in the UK. Pharmacies may provide the brand of each drug that is available to them, i.e. a specific brand is not required for the trial. Example manufacturers are:

Oral Cilostazol 100mg tables are manufactured by Generics [UK] Ltd t/a Mylan, [name], United Kingdom. (<http://www.mylan.co.uk>).

Oral Isotard® 25 mg XL (Isosorbide Mononitrate) tablets are manufactured by Kyona Kirin Limited, [name], United Kingdom. (<http://www.kyowa-kirin.com/kkr>)

Isosorbide mononitrate (ISMN) 20mg are manufactured by Pharmavit Ltd, [name] (<http://www.pharmavit.eu>)

6.1.3 Marketing Authorisation Holder

Details of one marketing authorisation holder of each of the trial drugs are given below.

Cilostazol 100mg tables - Generics [UK] Ltd t/a Mylan, [name], United Kingdom, under marketing authorisation number PL 04569/1426.

Isotard® 25 mg XL tablets – Kyowa Kirin Limited, [name], United Kingdom, under marketing authorisation number PL 16508/0018.

Isosorbide mononitrate (ISMN) 20mg tablets - Pharmavit Ltd, [name] (<http://www.pharmavit.eu>) under marketing authorisation number PL 04556/0057..

